#### **13.3. Subjects Confidentiality and Data Protection**

The investigator must take all appropriate measures to ensure that the anonymity of each study subject will be maintained. Subjects should be identified by a subject identification number only, on CRFs or other documents submitted to the sponsor. Documents that will not be submitted to the sponsor (eg, signed ICF) must be kept in strict confidence. Government agencies such as Health and Human Services, other health authorities, IRBs/ ECs, and staff/contractors may review these records, as appropriate.

The subject's and investigator's personal data, which may be included in the sponsor database, will be treated in compliance with all applicable laws and regulations. The sponsor shall take all appropriate measures to safeguard and prevent access to this data by any unauthorized third party.

### **13.4. Institutional Review Board/Ethics Committee**

An appropriately constituted IRB/EC, as described in ICH guidelines for GCP, must review and approve:

- The protocol, ICF, and any other materials to be provided to the subjects (eg, advertising) before any subject may be enrolled in the study
- Any amendment or modification to the study protocol or ICF before implementation, unless the change is necessary to eliminate an immediate hazard to the subject, in which case the IRB/EC should be informed as soon as possible
- Ongoing studies on an annual basis or at intervals appropriate to the degree of risk

In addition, the IRB/EC should be informed of any event likely to affect the safety of subjects or the continued conduct of the clinical study.

A copy of the IRB/EC approval letter with a current list of the IRB/EC members and their functions must be received by the sponsor prior to shipment of drug supplies to the investigator. The approval letter should include the study number and title, the documents reviewed, and the date of the review.

Records of the IRB/EC review and approval of all study documents (including approval of ongoing studies) must be kept on file by the investigator.

### **13.5. Clinical Study Data Transparency**

Final study results will be published on a public clinical trial website according to applicable local guidelines and regulations. Treatment codes will be disseminated to each investigation site thereafter.

## **14. PROTOCOL AMENDMENTS**

The sponsor may not implement a change in the design of the protocol or ICF without an IRB/EC-approved amendment. Where required per local legislation, regulatory authority approval will also be sought.

## 15. PREMATURE TERMINATION OF THE STUDY OR CLOSE-OUT OF A SITE

### 15.1. Premature Termination of the Study

The sponsor has the right to terminate the study prematurely. Reasons may include efficacy, safety, or futility, among others. Should the sponsor decide to terminate the study, the investigator(s) will be notified in writing.

### 15.2. Close-out of a Site

The sponsor and the investigator have the right to close-out a site prematurely.

#### Investigator's Decision

The investigator must notify the sponsor of a desire to close-out a site in writing, providing at least 30 days' notice. The final decision should be made through mutual agreement with the sponsor. Both parties will arrange the close-out procedures after review and consultation.

#### Sponsor's Decision

The sponsor will notify the investigator(s) of a decision to close-out a study site in writing. Reasons may include the following, among others:

- The investigator has received all items and information necessary to perform the study, but has not enrolled any subject within a reasonable period of time
- The investigator has violated any fundamental obligation in the study agreement, including but not limited to, breach of this protocol (and any applicable amendments), breach of the applicable laws and regulations, or breach of any applicable ICH guidelines
- The total number of subjects required for the study are enrolled earlier than expected

In all cases, the appropriate IRB/EC and Health Authorities must be informed according to applicable regulatory requirements, and adequate consideration must be given to the protection of the subjects' interests.

## 16. CONFIDENTIALITY

Confidentiality of information is provided as a separate agreement.

## 17. FINANCING AND INSURANCE

Financing and insurance information is provided as a separate agreement.

## 18. PUBLICATION POLICY

Publication rights and procedures will be outlined in a separate clinical study agreement.

PCSV	Potentially clinically significant value
RBC	Red blood cell
RBD	Receptor binding domain
RT-qPCR	Quantitative reverse transcription polymerase chain reaction (test; refers to the central lab testing in this protocol)
SARS-CoV-2	Severe acute respiratory syndrome coronavirus 2
SAE	Serious adverse event
SAF	Safety analysis set
SAP	Statistical analysis plan
SAS	Statistical Analysis System
SC	Subcutaneous
SD	Standard deviation
SOC	System organ class
TEAE	Treatment-emergent adverse event
WBC	White blood cell
WHO	World Health Organization
WOCBP	Women of childbearing potential

1. OVERVIEW

The purpose of the statistical analysis plan (SAP) is to ensure the credibility of the study results by pre-specifying the statistical approaches for the analysis of study data prior to database lock and unblinding. The SAP is intended to be a comprehensive and detailed description of the strategy and statistical methods to be used in the analysis of data for R10933-10987-COV-2069 study. The SAP includes multiple steps of analyses described in Section 7.

This plan may be revised during the study to accommodate protocol amendments and/or to make changes to adapt to unexpected issues in study execution and/or data that affect planned analyses. These revisions will be based on blinded data review, and a final plan will be issued prior to the first step database lock and unblinding of the individual treatment assignment.

1.1. Background/Rationale

This study will assess the use of REGN10933+REGN10987 in preventing household transmission of SARS-CoV-2. A household is defined as a group of people who live together at the same residence and share multiple living spaces (e.g., living room, bedroom, kitchen, bathroom).

1.2. Study Objectives

All subjects in the study will have household contact with the first household member known to be infected with SARS-CoV-2 infection (index case) but who are themselves either not infected or who are asymptomatic (having no active respiratory or non-respiratory symptoms consistent with COVID-19) at the time of screening. In this study, the household contact must share the same residence and have a close exposure to the first individual in the household with a known SARS-CoV-2 infection (index case).

For the analyses, there are four cohorts defined based on the subject's SARS-CoV-2 infection status at baseline, as measured by central lab SARS-CoV-2 RT-qPCR (quantitative reverse transcription polymerase chain reaction), and on the subject's age:

- For subjects with SARS-CoV-2 RT-qPCR negative at baseline, they are assigned into two cohorts:
 - Cohort A (adult and adolescent subjects [≥ 12 years])
 - Cohort A1 (pediatric subjects [< 12 years])

or

- For subjects with SARS-CoV-2 RT-qPCR positive at baseline, they are assigned into two cohorts:
 - Cohort B (adult and adolescent subjects [≥ 12 years])
 - Cohort B1 (pediatric subjects [< 12 years])

1.2.1. Primary Objectives

The primary objectives are for subjects who are seronegative at baseline (based on central lab test) unless stated otherwise.

Efficacy – Cohort A (Adult and adolescent subjects (≥ 12 years) who are SARS-CoV-2 RT-qPCR negative at baseline)

- To evaluate the efficacy of REGN10933+REGN10987 compared to placebo in preventing symptomatic SARS-CoV-2 infection (broad-term) confirmed by RT-qPCR

Efficacy – Cohort B (Adult and adolescent subjects (≥ 12 years) who are SARS-CoV-2 RT-qPCR positive at baseline)

- To evaluate the efficacy of REGN10933+REGN10987 compared to placebo in preventing COVID-19 symptoms (broad-term)

Safety – Cohort A and Cohort A1, Cohort B and B1

To evaluate the safety and tolerability of REGN10933+REGN10987 following subcutaneous (SC) administration compared to placebo

1.2.2. Secondary Objectives

Cohort A and Cohort A1

The following secondary objectives are for subjects who are seronegative at baseline (based on central lab test) unless stated otherwise.

- To evaluate the efficacy of REGN10933+REGN10987 compared to placebo in preventing a SARS-CoV-2 infection with a high viral load (i.e. viral load >4 (log₁₀ copies/mL))
- To evaluate the impact of REGN10933+REGN10987 compared to placebo on the duration of signs and symptoms in subjects with symptomatic SARS-CoV-2 infection (broad-term) confirmed by RT-qPCR
- To evaluate the impact of REGN10933+REGN10987 compared to placebo on the duration of SARS-CoV-2 infection with a high viral load (i.e. viral load >4 (log₁₀ copies/mL))
- To evaluate the impact of REGN10933+REGN10987 compared to placebo on the duration of SARS-CoV-2 infection
- To evaluate the efficacy of REGN10933+REGN10987 compared to placebo in preventing asymptomatic or symptomatic SARS-CoV-2 infection confirmed by RT-qPCR
- To evaluate the impact of treating the index case with REGN10933+REGN10987 on the incidence of SARS-CoV-2 infection among their household contacts in placebo group (note: This is a cross-study analysis based on only subjects in placebo group of R10933-10987-COV-2069 whose index cases participated in R10933-10987-COV-2067)

- To evaluate the efficacy of REGN10933+REGN10987 compared to placebo in preventing symptomatic SARS-CoV-2 infection (Centers for Disease Control and Prevention (CDC) definition) confirmed by RT-qPCR
- To evaluate the efficacy of REGN10933+REGN10987 compared to placebo in preventing symptomatic SARS-CoV-2 infection (strict-term) confirmed by RT-qPCR
- To evaluate the impact of REGN10933+REGN10987 compared to placebo on SARS-CoV-2 RT-qPCR viral load
- To evaluate the impact of REGN10933+REGN10987 compared to placebo on SARS-CoV-2 infection:
 - On health care utilization
 - On absenteeism from daily responsibilities (where applicable)
- To evaluate the impact of treating any SARS-CoV-2 RT-qPCR positive household member with REGN10933+REGN10987 on the incidence of SARS-CoV-2 infection among their household contacts in placebo group (note: This is a cross-study analysis based on only subjects in placebo group of R10933-10987-COV-2069 whose index or other household member participated in R10933-10987-COV-2067 or in cohort B)
- To characterize the drug concentration-time profiles of REGN10933 and REGN10987 in serum and selected PK parameters
- To assess the immunogenicity of REGN10933 and REGN10987
- To evaluate the safety and tolerability of REGN10933+REGN10987 following SC administration in seropositive subjects
- To estimate the incidence and severity of symptomatic SARS-CoV-2 infection over time, including the period following study drug treatment, in REGN10933+REGN10987-treated seronegative and seropositive subjects compared with placebo-treated subjects
- To evaluate the efficacy of REGN10933+REGN10987 compared to placebo in preventing symptomatic SARS-CoV-2 infection (broad-term) confirmed by RT-qPCR (cohort A1)

Cohort B and Cohort B1

Secondary objectives for Cohort B and Cohort B1 are for all seronegative subjects at baseline (by central lab test) unless stated otherwise.

- To evaluate the efficacy of REGN10933+REGN10987 compared to placebo in preventing development of:
 - Symptomatic SARS-CoV-2 infection (strict-term)
 - Symptomatic SARS-CoV-2 infection (broad-term; cohort B1)
 - Symptomatic SARS-CoV-2 infection (CDC definition)

- To evaluate the impact of REGN10933+REGN10987 compared to placebo on the duration of signs and symptoms in subjects with symptomatic SARS-CoV-2 infection confirmed by RT-qPCR
- To evaluate the impact of REGN10933+REGN10987 compared to placebo on the duration of SARS-CoV-2 infection with a high viral load
- To evaluate the impact of REGN10933+REGN10987 compared to placebo on SARS-CoV-2 viral load
- To evaluate the impact of REGN10933+REGN10987 compared to placebo in SARS-CoV-2 infection:
 - On health care utilization
 - On absenteeism from daily responsibilities (where applicable)
 - To characterize the drug concentration-time profiles of REGN10933 and REGN10987 in serum and selected PK parameters
 - To assess the immunogenicity of REGN10933 and REGN10987
 - To evaluate the safety and tolerability of REGN10933+REGN10987 following SC administration
 - To estimate the incidence and severity of symptomatic SARS-CoV-2 infection over time, including the period following study drug treatment, in REGN10933+REGN10987-treated subjects compared with placebo-treated subjects

1.2.3. Exploratory Objectives

Cohort A and Cohort A1

- To evaluate the efficacy of REGN10933+REGN10987 compared to placebo in preventing SARS-CoV-2 infection assessed by seroconversion in baseline seronegative subjects
- To explore the impact of REGN10987+REGN10933 compared to placebo:
 - On humoral immune response to SARS-CoV-2 infection
 - On measures of infectivity of SARS-CoV-2 as assessed in experimental laboratory assays
- To evaluate the impact of REGN10933+REGN10987 compared to placebo in SARS-CoV-2 infection in subjects who are seropositive at baseline:
 - Prevention of symptomatic infection (strict-term)
 - Prevention of symptomatic infection (broad-term)
 - Prevention of symptomatic infection (CDC definition)
 - Prevention of asymptomatic infection or symptomatic re-infection (strict-term, CDC definition, or broad-term)

- To explore the relationships between REGN10933+REGN10987 exposure and selected clinical efficacy and safety endpoints and/or biomarkers in seropositive and seronegative subjects
- To assess viral genetic variation in SARS-CoV-2 in subjects with a positive SARS-CoV-2 RT-qPCR
- To explore biomarkers (including host genome variants) associated with safety and efficacy of REGN10933+REGN10987 and to study SARS-CoV-2 (cohort A only)
- To evaluate the impact of treating any household member with anti-SARS CoV-2 monoclonal antibody on the incidence of SARS-CoV-2 infection among their household contacts. The monoclonal antibody treatment considered for this analysis are any EUA approved antibody including REGN10933+REGN10987 (within or outside of the study R10933-R10987-COV-2067)

Cohort B and Cohort B1

- To evaluate the impact of REGN10933+REGN10987 compared to placebo in seropositive subjects in preventing:
 - Symptomatic SARS-CoV-2 infection (strict-term)
 - Symptomatic SARS-CoV-2 infection (broad-term)
 - Symptomatic SARS-CoV-2 infection (CDC definition)
- To evaluate the impact of REGN10933+REGN10987 compared to placebo on the duration of signs and symptoms in seropositive subjects with symptomatic SARS-CoV-2 infection confirmed by RT-qPCR
- To evaluate the impact of REGN10933+REGN10987 compared to placebo in seropositive subjects on SARS-CoV-2 RT-qPCR viral load
- To evaluate the impact of REGN10933+REGN10987 compared to placebo in seropositive subjects on SARS-CoV-2 infection:
 - On health care utilization
 - On absenteeism from daily responsibilities (where applicable)
- To explore the impact of REGN10987+REGN10933 compared to placebo in subjects, by their baseline serology test status (e.g., seropositive or seronegative, based on central lab test) on SARS-CoV-2 infection:
 - On humoral immune response
 - On measures of infectivity of SARS-CoV-2 as assessed in experimental laboratory assays
- To explore the relationships between REGN10933+REGN10987 exposure and selected clinical efficacy and safety endpoints and/or biomarkers in seropositive and seronegative subjects

- To assess viral genetic variation in SARS-CoV-2 in subjects with a positive SARS-CoV-2 RT-qPCR.
- To explore biomarkers (including host genome variants) associated with safety and efficacy of REGN10933+REGN10987 and to study SARS-CoV-2

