**Virologic efficacy:** The primary mechanism of action of REGN10933+REGN10987 is blockade of the S protein RBD interaction with ACE2, leading to inhibition of SARS-CoV-2 host cell infection. The ability of REGN10933+REGN10987 treatment to prevent SARS-CoV-2 infection will be evaluated by SARS-CoV-2 RT-qPCR test results from weekly NP swab samples. Weekly sample collection is considered an adequate collection frequency to ensure early detection of viral load (SARS-CoV-2 RT-qPCR positivity) in infected individuals; this is based on the average duration of viral positivity from NP swabs that ranges from 7 to 28 days (He, 2020) (Wölfel, 2020). All subjects will have SARS-CoV-2 RT-qPCR testing by NP sample. Nasopharyngeal swab testing has been shown to have good sensitivity and specificity for detecting SARS-CoV-2 RNA (Zou, 2020) (Pere, 2020). The administrative assessment of seronegative subjects (n=409) in cohort A demonstrated that the risk of becoming infected (ie, becoming SARS-CoV-2 RT-PCR positive) was reduced as early as the first week of study (10.3% in subjects in the placebo group versus 5.4% in subjects in the REGN10933+REGN10987 group at day 8). The protection continued through the following weeks. Both the magnitude and duration of infection were reduced by REGN10933+REGN10987 treatment. Infections occurring in subjects in the placebo group had, on average, more than 100-fold higher peak viral load. Infections in subjects in the REGN10933+REGN10987 group lasted no more than 1 week, while approximately 40% of infections in subjects in the placebo group lasted 3 to 4 weeks. No infected subjects in the REGN10933+REGN10987 group had high viral loads ( $>10^4$  copies/mL) compared to 62% of the infected subjects in the placebo group (13/21 placebo versus 0/9 REGN10933+REGN10987) (CDC, 2020b). (CDC, 2020b)

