#### **4.1.4. Cohort A and Cohort A1 Exploratory Endpoints**

The exploratory endpoints for cohort A are:

- Proportion of baseline-seronegative subjects who have a first RT-qPCR confirmed SARS-CoV-2 infection in the follow-up period (ie, after day 29 visit)
- Proportion of baseline seronegative subjects who become seropositive (based on central lab test) up to day 57

- Proportion of baseline-seropositive subjects (based on central lab test) who subsequently have a positive SARS-CoV-2 RT-qPCR and symptomatic (strict-term) SARS-CoV-2 infection during the EAP
- Proportion of subjects with negative RT-qPCR (based on central lab test) regardless of the serology status at baseline who subsequently have a positive SARS-CoV-2 RT-qPCR and symptomatic (strict-term) SARS-CoV-2 infection during the EAP
- Proportion of baseline-seronegative or baseline-seropositive subjects with negative RT-qPCR (based on central lab test) who subsequently have a positive SARS-CoV-2 RT-qPCR and symptomatic (strict-term) SARS-CoV-2 infection during EAP
- Proportion of baseline-seropositive subjects (based on central lab test) who subsequently have a positive SARS-CoV-2 RT-qPCR and symptomatic (broad-term) SARS-CoV-2 infection during the EAP
- Proportion of subjects with negative RT-qPCR (based on central lab test) regardless of the serology status at baseline who subsequently have a positive SARS-CoV-2 RT-qPCR and symptomatic (broad-term) SARS-CoV-2 infection during the EAP
- Proportion of baseline-seronegative or baseline-seropositive subjects with negative RT-qPCR (based on central lab test) who subsequently have a positive SARS-CoV-2 RT-qPCR and symptomatic (broad-term) SARS-CoV-2 infection during the EAP
- Proportion of baseline-seropositive subjects (based on central lab test) who subsequently have a positive SARS-CoV-2 RT-qPCR and symptomatic (CDC definition) SARS-CoV-2 infection during the EAP
- Proportion of subjects with negative RT-qPCR (based on central lab test) regardless of the serology status at baseline who subsequently have a positive SARS-CoV-2 RT-qPCR and symptomatic (CDC definition) SARS-CoV-2 infection during the EAP
- Proportion of baseline-seronegative or baseline-seropositive subjects with negative RT-qPCR (based on central lab test) who subsequently have a positive SARS-CoV-2 RT-qPCR and symptomatic (CDC definition) SARS-CoV-2 infection during the EAP

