#### **9.2.6.2. Serological Assays for Endogenous Anti-SARS-CoV-2 Antibodies**

In order to assess the impact of baseline humoral immunity/antibody response to SARS-CoV-2 on REGN10933+REGN10987 efficacy to prevent SARS-CoV-2 infection, serum anti-SARS-CoV-2 will be measured at baseline, including but not limited to those which detect antibodies against the S protein and/or the N protein and/or neutralization assays. The impact of a positive serology result on drug efficacy will be assessed by associating seropositivity to positive SARS-CoV-2 RT-qPCR test from NP swabs. Association of seropositivity with clinical endpoints and other measures may also be explored.

To explore whether REGN10933+REGN10987 affect the generation of a humoral immune response to SARS-CoV-2, serum anti-SARS-CoV-2 N protein antibodies will be measured using immunoassays in REGN10933+REGN10987 groups as compared to placebo control, as well as to baseline.

Any unused samples may be kept for up 15 years after study completion for use in exploratory research (or for a shorter time period if required per regional laws and regulations).

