3.1. The Efficacy Analysis Sets

Seronegative Modified Full Analysis Set (Seronegative mFAS-A) – Cohort A

The seronegative modified full analysis set for Cohort A (Seronegative mFAS-A) includes all randomized subjects aged 12 years and older who are laboratory confirmed negative for SARS-CoV-2 (per central lab PCR test) and who test negative for antibodies for SARS-CoV-2 (per central lab serology testing) at baseline.

Subjects included in the administrative assessment analysis are excluded from the Seronegative mFAS-A population.

Subjects will be analyzed based on the randomized treatment assignment. The seronegative mFAS-A population is the primary analysis population for the primary and secondary endpoints for Cohort A of this study unless specified otherwise.

Note: There are three antibody assays used for serology test: EuroImmun anti-S IgA, EuroImmun anti-S IgG, and Abbott anti-N IgG (Architect). Seronegative is defined as all available test results are negative. Seropositive is defined as 1 or more available test results are positive.

Seronegative Modified Full Analysis Set (Seronegative mFAS-A1) – Cohort A1

The seronegative modified full analysis set for Cohort A1 (seronegative mFAS-A1) includes all randomized subjects aged less than 12 years who are laboratory confirmed negative for SARS-CoV-2 (per central lab PCR test) and who test negative for antibodies for SARS-CoV-2 (per central lab serology testing) at baseline.

Subjects will be analyzed based on the randomized treatment assignment. The efficacy endpoints for Cohort A1 will be analyzed using the seronegative mFAS-A1 unless specified otherwise.

Seronegative Modified Full Analysis Set (Seronegative mFAS-B) – Cohort B

The seronegative modified full analysis set for Cohort B (seronegative mFAS-B) includes all randomized subjects aged 12 years and older who have laboratory confirmed positive tests at baseline for SARS-CoV-2 RT-qPCR and negative SARS-CoV-2 serology (both based on central lab testing) at baseline and are asymptomatic. Subjects will be analyzed based on the randomized treatment assignment. The primary and secondary efficacy endpoints for cohort B will be analyzed using the seronegative mFAS-B unless specified otherwise.

Seronegative Modified Full Analysis Set (Seronegative mFAS-B1) – Cohort B1

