4.5.4. Cohort A and Cohort A1 Exploratory Efficacy Variables

The following exploratory variables are for both Cohort A and Cohort A1. Some of the endpoints will mature and be assessed after all subjects complete the study. For continuous variables the analysis only applies to subjects who have a positive central lab SARS-CoV-2 RT-qPCR test (based on observed data) during the EAP.

Exploratory Variables	Type
Proportion of baseline-seronegative subjects who have a first RT-qPCR confirmed SARS-CoV-2 infection in the follow-up period (i.e. after Day 29 visit)	B
Proportion of baseline-seronegative subjects who become seropositive (based on central lab test) up to day 57 (Note: For post-treatment serology, only antibody assay(s) that do not bind to REGN10933 or REGN10987 will be used to define the endpoint)	B
Proportion of baseline-seropositive subjects (based on central lab test) who subsequently have a positive SARS-CoV-2 RT-qPCR and symptomatic (strict-term) SARS-CoV-2 infection during the EAP	B
Proportion of subjects with negative RT-qPCR (based on central lab test) regardless of the serology status at baseline who subsequently have a positive SARS-CoV-2 RT-qPCR and symptomatic (strict-term) SARS-CoV-2 infection during the EAP	B

Proportion of baseline-seronegative or baseline-seropositive subjects with negative RT-qPCR (based on central lab test) who subsequently have a positive SARS-CoV-2 RT-qPCR and symptomatic (strict-term) SARS-CoV-2 infection during the EAP	B
Proportion of baseline-seropositive subjects (based on central lab test) who subsequently have a positive SARS-CoV-2 RT-qPCR and symptomatic (broad-term) SARS-CoV-2 infection during the EAP	B
Proportion of subjects with negative RT-qPCR (based on central lab test) regardless of serology status at baseline who subsequently have a positive SARS-CoV-2 RT-qPCR and symptomatic (broad-term) SARS-CoV-2 infection during the EAP	B
Proportion of baseline-seronegative or baseline-seropositive subjects with negative RT-qPCR (based on central lab test) who subsequently have a positive SARS-CoV-2 RT-qPCR and symptomatic (broad-term) SARS-CoV-2 infection during the EAP	B
Proportion of baseline-seropositive subjects (based on central lab test) who subsequently have a positive SARS-CoV-2 RT-qPCR and symptomatic (CDC definition) SARS-CoV-2 infection during the EAP	B

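### The exploratory seroconversion endpoint cannot by itself show that infection was prevented, because it mixes infection risk with the chance of seroconverting once infected

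*SAP*

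**What the plan says.** SAP 1.2.3 (and Protocol 2.1.4) lists among the exploratory objectives for Cohorts A and A1: "To evaluate the efficacy of REGN10933+REGN10987 compared to placebo in preventing SARS-CoV-2 infection assessed by seroconversion in baseline seronegative subjects". The matching endpoint in Protocol 4.1.4 is "Proportion of baseline seronegative subjects who become seropositive (based on central lab test) up to day 57". SAP 4.5.4 repeats it and adds a restriction: "Note: For post-treatment serology, only antibody assay(s) that do not bind to REGN10933 or REGN10987 will be used to define the endpoint".

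SAP 3.1 names the assays: "There are three antibody assays used for serology test: EuroImmun anti-S IgA, EuroImmun anti-S IgG, and Abbott anti-N IgG (Architect"). Both drug antibodies bind the spike protein (Protocol 1.4).

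The next exploratory objective in SAP 1.2.3 concerns the effect of the drug "On humoral immune response to SARS-CoV-2 infection". Protocol 9.2.6.2 says how this will be examined: "To explore whether REGN10933+REGN10987 affect the generation of a humoral immune response to SARS-CoV-2, serum anti-SARS-CoV-2 N protein antibodies will be measured using immunoassays", with the drug group compared with placebo and with baseline. Protocol 3.3 lists interference with the endogenous immune response to infection among theoretical risks.

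SAP 5.7.4 carries the key secondary methods over to exploratory endpoints where appropriate, and permits nominal p-values. It rules out hypothesis testing for Cohort A1.

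**The concern.** The objective treats seroconversion as a stand-in for infection. That works for comparing arms only if an infected subject is equally likely to seroconvert in either arm. The plan leaves this open: it asks in a separate objective whether the drug changes the humoral response, and uses the same antibody to find out.

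The administrative assessment gives a further reason not to assume equality. Protocol 3.2.6 says "Infections in subjects in the REGN10933+REGN10987 group lasted no more than 1 week", while about 40% of placebo infections lasted 3 to 4 weeks. Peak viral load in placebo infections was on average more than 100-fold higher. High viral load occurred in 13 of 21 infected placebo subjects and 0 of 9 infected drug subjects. Smaller, shorter infections might leave less anti-N antibody.

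The SAP 4.5.4 restriction guards against one error, namely reading the injected antibody as seropositivity. It does nothing about the opposite error, an infected drug-arm subject who does not convert. Neither document plans anti-N conversion by arm among RT-qPCR-confirmed infections, or cautions the reader. At stake is the interpretation of one supporting result, which could pass for independent confirmation of the RT-qPCR finding.

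**Working it through.** **1. Which assay remains.** There are three assays: anti-S IgA, anti-S IgG and anti-N IgG (SAP 3.1). The drug is anti-S (Protocol 1.4), and assays that bind it are excluded (SAP 4.5.4). That leaves anti-N IgG. This is an inference, since the endpoint text does not name the assay.

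**2. The plan's own figures.** The documents give no power or rate for the seroconversion endpoint, so only the design inputs can be checked (SAP 2.2.1: 1248 seronegative subjects, 10% versus 5%, two-sided 0.05; 1:1 allocation gives 624 per arm).

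- Power = Φ{[d − 1.96·√(2p̄(1−p̄)/n)] / √[(p₀(1−p₀)+p₁(1−p₁))/n]}, with d = 0.05, p̄ = 0.075 and n = 624. This is Φ[(0.05 − 0.0292)/0.0148] = 0.919. The SAP gives 0.914 at the lowest household correlation.
- Enrolment: 1248/(0.70 × 0.90) = 1981. The SAP gives 1980.
- Odds ratio: (0.05/0.95)/(0.10/0.90) = 0.474. The SAP gives 0.47.

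The inputs reproduce.

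**3. What the endpoint measures.** In each arm, ignoring false positives,

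P(seroconvert) = P(infected) × P(anti-N positive given infected).

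The ratio between arms is the infection risk ratio multiplied by the ratio of conversion probabilities. With equal infection risk, the whole apparent effect is the second factor.

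**4. Size under equal infection.** Assumed, not in the documents: 90% anti-N conversion among infected placebo subjects, and the active-arm values shown. The test is two-sided Fisher at 0.05, 624 independent subjects per arm, by exact enumeration.

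| Conversion if infected, active arm | Apparent RR | Nominal p<0.05, 10% infected in each arm | Nominal p<0.05, 5% infected in each arm |
|---|---|---|---|
| 90% | 0.90/0.90 = 1.00 | 4.0% | 3.7% |
| 70% | 0.70/0.90 = 0.78 | 22.5% | 11.8% |
| 50% | 0.50/0.90 = 0.56 | 76.7% | 43.6% |
| 30% | 0.30/0.90 = 0.33 | 99.5% | 86.3% |

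For example, at 10% infection and 50% active conversion, 9.0% of placebo and 5.0% of drug subjects seroconvert, although infection is identical.

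**5. Wider range.** This uses the formula in step 2 and counts only results favouring the drug, with infection of 5% to 15% and placebo conversion of 70% to 100%. A 25% relative cut in conversion gives p<0.05 in 14% to 50% of trials. A 50% cut gives 49% to 99%.

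**6. If the drug does prevent infection.** With a true infection risk ratio of 0.5 and conversion cut by a fraction b, apparent efficacy is 1 − 0.5(1 − b): 50% at b = 0, 62.5% at b = 0.25 and 75% at b = 0.50.

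**The case against.** The strongest reply is that little depends on this endpoint. It is exploratory and outside the testing hierarchy. The hypotheses in SAP 5.7 and Protocol 11.1 cover primary and secondary endpoints only, so no null is stated for seroconversion, and a nominal p-value is the most that can follow. The infection test under type I error control is RT-qPCR-confirmed infection regardless of symptoms, fifth among the Cohort A key secondary endpoints (SAP 5.7.2). It comes from weekly swabs and does not depend on antibody response. If infection were truly equal, that result would stand beside any seroconversion difference. All of this stands. It limits the weight of the result but does not remove the bias.

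Second, a reader might infer that the sponsor accepts that the drug suppresses anti-N antibody. The documents do not say so. They speak of affecting and interfering with the response, give no direction or size for anti-N, and report no serology from the 9 drug-arm infections.

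Third, the figures rest on assumed conversion rates and on equal infection. The only data given run against equal infection: 21/223 = 9.4% versus 9/186 = 4.8%, a ratio of 0.51. Fisher's test on independent subjects also differs from the GEE or logistic model that the SAP would use. This too stands, and the figures show sensitivity to an untested assumption, not expected error rates.

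Fourth, the two objectives can draw on one antibody without contradiction, because one concerns response once infected and the other covers all baseline-seronegative subjects. That is fair, but the infected-only comparison that would tell them apart is not planned.

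**Conclusion.** The point holds as a limit on interpretation. As planned, a between-arm difference in seroconversion is not a clean estimate of infection prevention, because it combines infection risk with the chance of anti-N conversion given infection. The second factor may differ between arms, and no planned analysis examines it.

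The size cannot be fixed from the documents. Under the stated assumptions, active-arm conversion of 70% to 30% against 90% on placebo would produce apparent risk ratios of 0.78 to 0.33 with no infection prevented. At 10% infection, a nominal p<0.05 would follow in about 23% to over 99% of trials.

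A reader might infer that the trial's evidence on infection prevention is compromised, or that a false claim of prevention would follow. Neither is supported. The primary endpoint and the RT-qPCR infection endpoint are unaffected, and the RT-qPCR result carries the claim.

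**What to change.** In SAP 4.5.4 and 5.7.4:

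1. Report anti-N seroconversion up to day 57 by arm, separately for subjects who were RT-qPCR positive and RT-qPCR negative during the EAP. Note that the positive subset is defined after randomisation, so this comparison is descriptive.
2. Reword the objective, here and in SAP 1.2.3, so that seroconversion alone is not read as efficacy in preventing infection. State that it supports the RT-qPCR infection result only if conversion among RT-qPCR-positive subjects is similar between arms.

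Do not replace the endpoint with a composite of RT-qPCR positivity or seroconversion; at most, show the composite as a supplementary analysis. It reduces the bias but does not remove it. As an illustration, assume equal infection, independent detection, and conversion of 90% on placebo and 30% on drug. If RT-qPCR detects 80% of infections in both arms, the composite captures 1 − 0.2 × 0.1 = 0.98 on placebo and 1 − 0.2 × 0.7 = 0.86 on drug, a ratio of 0.88. If shorter infections lower RT-qPCR detection on drug to 50%, the drug figure is 1 − 0.5 × 0.7 = 0.65 and the ratio is 0.66.

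The cost is two small descriptive tables from swabs and serology already scheduled, and a more limited claim for one exploratory endpoint.
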